9.3. Joint Investigator/Sponsor Responsibilities

9.3.1. Access to Information for Monitoring

In accordance with ICH Good Clinical Practice (ICH GCP) guidelines, the study monitor must have direct access to the investigator's source documentation in order to verify the data recorded in the CRFs for consistency.

The monitor is responsible for routine review of the CRFs at regular intervals throughout the study to verify adherence to the protocol and the completeness, consistency, and accuracy of the data being entered on them. The monitor should have access to any subject records needed to verify the entries on the CRFs. The investigator agrees to cooperate with the monitor to ensure that any problems detected in the course of these monitoring visits are resolved.

9.3.2. Access to Information for Auditing or Inspections

Representatives of regulatory authorities or of Gilead Sciences may conduct inspections or audits of the clinical study. If the investigator is notified of an inspection by a regulatory authority the investigator agrees to notify the Gilead Sciences medical monitor immediately. The investigator agrees to provide to representatives of a regulatory agency or Gilead Sciences access to records, facilities, and personnel for the effective conduct of any inspection or audit.

9.3.3. Study Discontinuation

Both the sponsor and the investigator reserve the right to terminate the study at any time. Should this be necessary, both parties will arrange discontinuation procedures and notify the appropriate regulatory authority(ies), IRBs, and IECs. In terminating the study, Gilead Sciences and the investigator will assure that adequate consideration is given to the protection of the subjects' interests.

9.4. Independent Review Committee

An IRC will be established to provide a review of radiographic data and pertinent clinical data in order to provide expert interpretation of changes in tumor status. The IRC will include ≥ 1 independent board-certified radiologist and ≥ 1 independent board-certified hematologist or oncologist, and will be managed by a CRO selected by Gilead Sciences. The review of radiographic and clinical data by the IRC will be performed on an ongoing basis. The specifics of the IRC's processes and reading methods will be described in an independent review charter developed by the contracted central imaging vendor in conjunction with Gilead Sciences.

11. APPENDICES

- Appendix 1. Investigator Signature Page
- Appendix 2. Study Procedures Table

Appendix 2. Study Procedures Table

Study Phase	Screening	Cycle 1 (28 days)	Subsequent Cycles (28 days)	Safety Monitoring Visits	Tumor Response Assessments	Disease Progression or EOS ^c	30-Day Follow Up
Cycle Day	Screening	1	1	Varies ^a	Q8 or 12 wks or 6 months ^b	N/A	
Window	-35		±2 days	±2 days		N/A	
Study Assessments							
Informed Consent	X						
Medical History	X						
Physical Exam ^d	X	X	X	X		X	
Vital Signs ^e	X	X	X	X		X	
12-lead ECG	X			X			
Karnofsky Performance Status	X	X	X	X		X	
Prior/Concomitant Meds	X	X	X	X		X	
AEs ^f	X	X	X	X		X	X
CT or MRI	X ^g				X ^h	X ⁱ	
Bone Marrow Biopsy and Aspirate					X ^j	X ^j	
DLBCL Subtyping ^k		X					
Collect Archival Tumor Tissue (if available)		X ^l					
Complete Subject/Visit info in IxRS	X	X	X			X	
Sample Collection							
Chemistry	X	X	X ^x	X		X	
Beta-2-microglobulin		X	X			X	
Hematology	X	X	X ^x	X		X	
Coagulation	X	X	X ^x	X		X	
Urinalysis	X	X	X				
HBV, HCV and HIV Virology	X						

Study Phase	Screening	Cycle 1 (28 days)	Subsequent Cycles (28 days)	Safety Monitoring Visits	Tumor Response Assessments	Disease Progression or EOS ^c	30-Day Follow Up
Cycle Day	Screening	1	1	Varies ^a	Q8 or 12 wks or 6 months ^b	N/A	
Window	-35		±2 days	±2 days		N/A	
Pregnancy Test ⁿ	X	X	X	X		X	
GS-9973 Plasma Concentration ^{o, p, v}		X	X	X		X	
Buccal Swab ^u		X					
CCI							
Serum monoclonal IgM SPEP/IFE and cryoglobulin testing ^q		X			X		
Study Drug Dosing							
GS-9973 up to 800 mg BID Fasting or 100, 200 or 400 mg GS-9973 SDD BID Fasting			X-----X				
Dispense Study Drug		X	X				
Study Drug Compliance ^r		X	X			X	
Collect Used/Unused Study Drug ^w			X			X	
For CLL, SLL and MCL subjects only							
Cytokines and Chemokines		X ^m	X ^m	X ^m		X	
CTC Molecular Characterization		X		X ^s		X	
CTC RNA ^w		X ^w	X ^w			X ^w	
CLL ONLY: Pharmacodynamic Measurements (BAT Assay)		X ^t					
CLL ONLY: Pharmacogenomic Testing		X		X ^s		X	

a Days 8, 15, and 22 of Cycle 1 and Day 15 of Cycle 2

b Tumor assessments will be performed every 8 weeks during the first 24 weeks of the study and then every 12 weeks thereafter regardless of cycle number and regardless of dose interruptions. Tumor assessments may be performed at other timepoints during the treatment phase as clinically indicated (to assess tumor progression). After week 72 scans will occur at least every 6 months (± 4 weeks). The same evaluation procedures must be used throughout the study for each subject. Scans should be of high quality and digitized in the DICOM format to allow for reading at a centralized facility.

- c If a subject stops study drug for a reason other than progressive disease and consistent with good medical practice, they will be followed as per the scheduled imaging in Section 6.5 with additional CBC (hematology) at time of assessments.
- d Complete physical examination will be performed at Screening and at Disease Progression or EOS. A modified physical examination capturing changes from prior exams will be performed at other visits. Weight should be measured (in kilograms) at each physical examination. Height will be measured (in centimeters) at Screening only.
- e Vital signs (including blood pressure, respiratory rate, pulse, oxygen saturation by pulse oximetry and temperature) should be taken after the subject has been sitting for at least 5 minutes.
- f Adverse events will be assessed once ICF is signed, pre- and post-dose during applicable clinic visits, and 30 (± 7) days following completion of the subject's last dose of study drug. Subjects should be contacted by phone (or in person, if necessary) 30 days (± 7 days) after the subject's last dose of study drug to assess AEs. Subjects should specifically be asked about the development of any adverse events since stopping the study.
- g CT or MRI scans of neck, chest, abdomen, and pelvis taken as part of standard medical practice up to 35 days prior to Day 1 of Cycle 1 visit are acceptable for use at the Screening. Subjects with LPL/WM who previously failed screening for this study, due to an absence of lymphadenopathy on CT or MRI scans, do not need to be re-scanned if the scans were performed within 16 weeks of first study drug administration to meet eligibility criteria.
- h At all timepoints after Screening imaging of the chest, abdomen, and pelvis will be required. Imaging of the neck is required at each follow-up time point if the neck scan was positive at baseline or if palpable neck lymphadenopathy appears during the course of the study.
- i Tumor evaluations should be conducted at the End of Study Visit if not conducted in the previous 4 weeks. If a subject permanently discontinues study drug prior to objective documentation of progression, investigators should continue further follow-up at the ~8 or ~12-week intervals until progression is documented.
- j A bone marrow biopsy and aspirate will be collected for all subjects who achieve a CR for confirmatory purpose. For CLL subjects a bone marrow biopsy/aspirate will be collected to confirm a PD. If the subject does not otherwise meet criteria for CR or if the nature of PD does not require bone marrow confirmations, it is not necessary to obtain a bone marrow biopsy/aspirate (See Sections 6.18 and 6.20).
- k If the subject has DLBCL, subtyping is required. Submission of 15 unstained slides is required for subtyping if the subtype is not already known. Subjects for whom tissue is not available but the subtype is already known may be included if approved by the Medical Monitor following discussion with the investigator.
- l Fifteen recently prepared unstained slides from archival tumor tissues will be collected. Efforts to acquire tissue sample should begin on Day 1 of Cycle 1.
- m Collect on Cycle 1 Day 1, Cycle 1 Day 8, Cycle 2 Day 1 and Cycle 12, Day 1 only
- n For females of childbearing potential, a serum pregnancy test will be performed at Screening and urine pregnancy tests will be performed on Days 1 of each Cycle and Day 15 of Cycles 1 & 2 and at EOS.
- o Record the approximate number of hours between the last 2 doses of GS-9973 and the time the blood samples for plasma concentration were obtained
- p GS-9973: PK samples will be collected on Day 1 of Cycle 1 pre-dose, 1.5 hours post-dose and 4 hours post-dose; on Day 1 of Cycles 2-6 pre-dose (12 hours post last dose). GS-9973 SDD: PK samples will be collected on Day 1 of Cycle 1 pre-dose, 1.5 hours post-dose and 4 hours post-dose; on Day 8 of Cycle 1 pre-dose, 1.5 hours post-dose and 4 hours post-dose; on Days 15 and 22 of Cycle 1 pre-dose and 1.5 hours post-dose; and on Day 1 of subsequent cycles pre-dose and 1.5 hours post-dose.
- q Subjects with LPL/WM only. This procedure should be conducted on the Day 1 visit occurring during the week window allotted for tumor response assessments.
- r Includes date/time of last dose of GS-9973 (excluding Day 1 of Cycle 1)
- s Collect on Cycle 2, Day 15 only
- t On Day 1 of Cycle 1, samples will be collected pre-dose, 1.5 hours post-dose (± 10 minutes) and 4 hours post-dose (± 10 minutes); on cycle 1 day 8 (predose and 4 hours post dose) and cycle 1 day 15 (predose)
- u For CLL dose ranging, CLL prior BTK inhibitor exposure, or CLL prior PI3K inhibitor exposure cohorts only
- v Excluding subjects off study drug at time of progression
- w Samples will be collected pre-dose on Cycle 1 Day 1, Cycle 12 Day 1 and at Disease Progression or EOS only
- x May be collected up to 2 days prior to the Day 1 visit

## LIST OF ABBREVIATIONS

AE	adverse event
ATC	Anatomical-Therapeutic-Chemical (drug coding system)
BCR	B-cell receptor
BID	twice a day
BLQ	below the limit of quantitation
BMI	body mass index
BOR	best overall response
CI	confidence interval
CLL	chronic lymphocytic leukemia
CR	complete response
eCRF	electronic case report form
CRF	case report form
CSR	clinical study report
CT	computerized tomography
CTCAE	Common Terminology Criteria for Adverse Events
CV	coefficient of variation
DLBCL	diffuse large B-cell lymphoma
DOR	duration of response
ECG	electrocardiogram
ENTO	Entospletinib
FL	follicular lymphoma
HLGT	high-level group term
HLT	high-level term
iNHL	indolent non-Hodgkin lymphoma
IRC	independent review committee
LOQ	lower limit of quantification
LLT	low level term
LPL	lymphoplasmacytoid lymphoma
MedDRA	Medical Dictionary for Regulatory Activities
MCL	mantle cell lymphoma
MM	mono-mesylate
MRI	magnetic resonance imaging
MZL	marginal zone lymphoma
ND	no disease
NE	not evaluable
NHL	non-Hodgkin lymphoma
ORR	objective response rate
PD	progressive disease
PFS	progression-free survival

---

PK	pharmacokinetic
PPI	proton pump inhibitors
PR	partial response
PT	preferred term
QTc	QT interval corrected
QTc-B	QT interval corrected for heart rate using Bazett's formula
QTc-F	QT interval corrected for heart rate using Fridericia's formula
SAE	serious adverse event
SAP	statistical analysis plan
SD	stable disease
SDD	spray dried dispersion
SE	standard error
SLL	small lymphocytic lymphoma
StD	standard deviation
SOC	system organ class
SPD	sum of the product of the diameters (of nodal or tumor masses)
SPEP	serum protein electrophoresis
TEAE	treatment-emergent adverse event
TLF	tables, figures, and listings
TTR	time to response
WHO	World Health Organization
WM	Waldenström macroglobulinemia

## 1. INTRODUCTION

This statistical analysis plan (SAP) describes the statistical analysis methods and data presentations to be used in tables, figures, and listings (TFLs) in the clinical study report (CSR) for Study GS-US-339-0102. This SAP is based on the study protocol Amendment 8 dated 31 March 2017 and the electronic case report form (eCRF). The SAP will be finalized before database finalization. Any changes made after the finalization of the SAP will be documented in the CSR.

Based on the Sponsor's strategic plan for entospletinib development, the CSR will be in synoptic version.

### 1.1. Study Objectives

The primary objective of this study is as follows:

- To evaluate the efficacy of entospletinib (ENTO; GS-9973) in subjects with relapsed or refractory hematologic malignancies

The secondary objectives of this study are as follows:

[figure not shown]
- To evaluate the safety and tolerability of ENTO in subjects with relapsed or refractory hematologic malignancies
- To evaluate ENTO exposures in subjects with relapsed or refractory hematologic malignancies

### 1.2. Study Design

#### 1.2.1. Design Configuration

This is a Phase 2, open-label study evaluating the efficacy, safety, and tolerability of ENTO administered twice daily (BID) over multiple 28-day cycles in subjects with relapsed or refractory hematologic malignancies. Historically the study planned to investigate 5 cohorts of ENTO in subjects with chronic lymphocytic leukemia (CLL), mantle cell lymphoma (MCL), diffuse large B-cell lymphoma (DLBCL), follicular lymphoma (FL), and a fifth cohort consisting of the non-FL indolent non-Hodgkin lymphomas (iNHL), ie, subjects with lymphoplasmacytoid lymphoma/Waldenström macroglobulinemia (LPL/WM), small lymphocytic lymphoma (SLL), or marginal zone lymphoma (MZL), with a mono-methanesulfonate salt at 800 mg bid of the original mono-mesylate (MM) formulation (Figure 1-1). After completion of enrollment of the original CLL cohort, the study was amended to include the addition of 3 CLL cohorts (1 dose finding prior B-Cell receptor (BCR) naïve cohort and 2 prior BCR exposure cohorts [ie, 1 prior BTK inhibitor and 1 prior PI3K inhibitor cohort]). All 3 additional cohorts receive a new formulation of ENTO designated spray dried dispersion (SDD). The SDD formulation had greater bioavailability and lesser drug-drug interactions (no H2 and reduce proton pump inhibitors (PPI)). As of protocol amendment 8, subjects receiving ENTO MM formulation are transitioned to the ENTO SDD formulation.

**Figure 1-1. Study Schema**

The 2 CLL cohorts with prior BCR exposure enroll based on the most recent progression followed BCR-exposure. The BCR naïve patient cohort designated as CLL dose ranging cohort are randomly assigned to one of 3 doses evaluating 100 mg, 200 mg, and 400 mg (200 mg x 2) BID dosing of ENTO SDD (Table 1-1).

**Table 1-1. Dose Levels and Formulations**

Cohort	Dose (BID)*	Formulation
CLL	800mg Amendment 8: 400mg	MM Amendment 8: SDD
MCL	800mg Amendment 8: 400mg	MM Amendment 8: SDD
DLBCL	800mg Amendment 8: 400mg	MM Amendment 8: SDD
FL	800 mg Amendment 8: 400mg	MM Amendment 8: SDD
Other iNHL (LPL/WM, SLL, and MZL)	800mg Amendment 8: 400mg	MM Amendment 8: SDD
CLL prior BCR inhibitor naïve	400mg 200mg 100mg	SDD SDD SDD
CLL Prior BTK inhibitor	400mg	SDD
CLL Prior PI3K inhibitor	400mg	SDD

\*Note 800mg of MM is PK/PD equivalent of 400 mg SDD

### 1.2.2. **CLL (non-dose-ranging cohorts), MCL, DLBCL, and FL cohorts**

A Bayesian, continuous data review approach is used to update the estimates of progression-free survival (PFS) rates at 16 weeks (CLL after BCR targeted therapy, MCL, and DLBCL) or 24 weeks (CLL and FL) for a malignancy. The data reviews for the CLL prior BTK inhibitor exposure and CLL prior PI3K inhibitor exposure cohorts are conducted independently for Richter's and non-Richter's. The criterion used for the futility boundary is defined as highly likely (>90%) that the PFS rates at 16 weeks (CLL after BCR targeted therapy, MCL, and DLBCL) or 24 weeks (CLL and FL) are less than 0.2 given the available subjects' efficacy data.

[figure not shown]
Futility assessment begins when the first 10 subjects' primary endpoints become available. Thereafter, continuous data reviews are conducted when a new primary endpoint becomes available.

- If the futility criterion is not met, subsequent subjects will be enrolled until a total of pre-defined number of subjects are recruited for a cohort.
- If the futility criterion is met, the sponsor will consider terminating enrollment to that malignancy, taking into account efficacy, drug exposure and subtype (for DLBCL), unless there are subjects who remain on treatment and have not yet reached 16 weeks (CLL after BCR targeted therapy, MCL, and DLBCL) or 24 weeks (CLL and FL). In this case, enrollment will be suspended until the next on-going subjects' primary endpoints become available, and another data review is conducted. If, after review of all available subjects, the futility boundary has still been crossed and the lack of drug exposure or for DLBCL, subtype does not explain the lack of activity, enrollment to that malignancy will be terminated.

The futility boundary is provided in [Figure 1-2](#) with details in [Section 2.1](#). The boundary is represented in terms of the total number of subjects and the number of progression-free subjects at Week 16 (CLL after BCR targeted therapy, MCL, and DLBCL) or Week 24 (CLL and FL). Subjects who withdraw or are lost to follow-up before Week 16 (CLL after BCR targeted therapy, MCL, and DLBCL) or week 24 (CLL and FL) will be considered as not achieving PFS for the analysis.

At each data review, if the observed ratio of the number of PFS at Week 16 (CLL after BCR targeted therapy, MCL and DLBCL) or Week 24 (CLL and FL) over the total number of subjects is at or below the futility boundary, the futility criterion has been met.

**Figure 1-2. Futility Boundary with Prior Distribution Beta (0.5, 1.5)**

**1.2.3. CLL Dose Ranging Cohort**

For the CLL dose ranging cohort, subjects are randomized in the ratio of 1:1:1 to receive 100 mg, 200 mg or 400 mg (200 mg x 2) of ENTO SDD BID. 20 subjects are planned to be treated at each of the three dose levels. Because the CLL dose ranging cohort consists of 3 different dose levels each with approximately 20 subjects, the continuation data review of futility will not be conducted for this cohort.

**1.2.4. Other iNHL (LPL/WM, SLL, and MZL) Cohort**

Because the ‘Other iNHL’ cohort consists of 3 different histologies, the accrual continues to a maximum of 45 subjects without a Bayesian analysis.

## **2. TYPE OF PLANNED ANALYSIS**

### **2.1. Final Analysis**

After all subjects have completed the study, outstanding data queries have been resolved or adjudicated as unresolvable, and the data have been cleaned and finalized, the final analysis of the data will be performed. Due to the Sponsor's strategic plan, the final CSR will be in synoptic version.

### **3. GENERAL CONSIDERATIONS FOR DATA ANALYSES**

Analysis results will be presented using descriptive statistics. For categorical variables, the number and percentage of subjects in each category will be presented; for continuous variables, the number of subjects (n), mean, standard deviation (StD) or standard error (SE), median, first quartile (Q1), third quartile (Q3), minimum, and maximum will be presented.

By-subject listings will be presented for all subjects in the All Enrolled Analysis Set and sorted by subject ID number, visit date, and time (if applicable). Data collected on log forms, such as AEs, will be presented in chronological order within the subject. The treatment group to which subjects are initially assigned will be used in the listings. Age, sex at birth, race, and ethnicity will be included in the listings, as space permits.

#### **3.1. Analysis Sets**

Analysis sets define the subjects to be included in an analysis. Analysis sets and their definitions are provided in this section. The analysis set will be identified and included as a subtitle of each table, figure, and listing.

##### **3.1.1. All Enrolled Analysis Set**

All Enrolled Analysis Set includes all subjects who received a study subject identification number in the study after screening. The All Enrolled Analysis Set will be used for subject enrollment summaries.

##### **3.1.2. Full Analysis Set**

The Full Analysis Set (FAS) includes all enrolled subjects who took at least one dose of study drug (ie, ENTO) with treatment group designated according to the planned treatment. This is the primary analysis set for efficacy analyses.

##### **3.1.3. Safety Analysis Set**

The Safety Analysis Set includes all subjects who took at least one dose of study drug (ie, ENTO) with treatment group designated according to the actual treatment. This is the primary analysis set for safety analyses.

##### **3.1.4. Pharmacokinetic Analysis Sets**

The Pharmacokinetic (PK) Analysis Set will include all enrolled subjects who took at least one dose of study drug (ie, ENTO) and have at least one nonmissing postdose concentration value reported by the PK laboratory. This is the primary analysis set for all PK analyses.

#### **3.2. Subject Grouping**

For summary tables, unless otherwise specified, subjects will be grouped by disease indications, prior treatment status, and dose levels as follows in [Table 3-1](#), [Table 3-2](#), and [Table 3-3](#).

**Table 3-1. Subject Grouping for Cohorts of CLL (except for the CLL Dose Ranging and the CLL after BCR Targeted Therapy Cohorts) and other Disease Indications**

CLL N = xx	FL N = xx	DLBCL N = xx	MCL N=xx	Other iNHL N = xx	Total N=xx
xx	xx	xx	xx	xx	xx

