A Bayesian, continuous data review approach using Beta-Binomial model will be used to update the estimates of progression-free survival (PFS) rates at 16 weeks (CLL after BCR targeted therapy, MCL and DLBCL) or 24 weeks (CLL and FL), assessing the efficacy once each subject's primary endpoint becomes available for a malignancy. The response is defined as subject not experiencing progression or death by week 16 (CLL after BCR targeted therapy, MCL and DLBCL) and 24 (CLL and FL). In this Beta-Binomial model, a binomial likelihood for the data and a conjugate Beta (0.5, 1.5) prior distribution for response rate θ are assumed. Statistical inference and decision-making will be based on the posterior distribution of response rate θ , which is a Beta distribution with parameters $x+0.5$ and $n-x+1.5$, where x is the observed number of subjects who achieve the response and n is the total number of subjects who have a response result for a given malignancy.

For the primary analysis of the primary efficacy endpoint, PFS will be described using Kaplan-Meier methods in the full analysis set. Medians, ranges, the proportion of subjects who are progression-free at Week 16 (CLL after BCR targeted therapy, MCL and DLBCL) and 24 (CLL and iNHL) will be presented. Data for subjects with iNHL will be presented by histologic subtype (ie, FL, SLL, LPL, and MZL). Data in the CLL prior BTK inhibitor exposed and prior PI3K inhibitor exposed cohort will be represented separately. Data in the CLL dose ranging cohort will be presented by dose level. The findings of the Independent Review Committee (IRC) will be considered primary for analyses of PFS. The full analysis set includes all subjects who receive ≥ 1 dose of GS-9973/GS-9973 SDD.

Sample Size Calculation

With the decision rule employed, and assuming that enrollment will be terminated once the futility criterion is met, a sample size of 40 subjects in a cohort gives this design a high probability (~84%) of claiming futility when the true response rate is low (0.1). When the true response rate is high (0.5), this design has a low probability (0.15%) of claiming futility.

This study will be conducted in accordance with the guidelines of Good Clinical Practice (GCP) including archiving of essential documents.

GLOSSARY OF ABBREVIATIONS AND DEFINITION OF TERMS

°C	degrees Celsius
°F	degrees Fahrenheit
ADR	adverse drug reaction
AE	adverse event
ALC	absolute lymphocyte count
ALT	alanine aminotransferase
AM	Morning

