3.1.3. LPL, SLL, MZL

Because the ‘other non-FL iNHL’ cohort consists of 3 different histologies, accrual will continue to a maximum of 45 subjects without a Bayesian analysis.

Figure 3-2. Futility Boundary with Prior Distribution Beta (0.5, 1.5)

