#### **6.1.2. Analysis of the Primary Efficacy Endpoint**

The primary analysis of PFS will be performed using the Kaplan-Meier (KM) method based on IRC response assessments for the FAS. Medians, Q1, Q3 of the PFS distributions, and the proportion of subjects who are progression-free at Week 16 (for CLL after BCR targeted therapy, MCL, and DLBCL) and Week 24 (for CLL and iNHL) from the first dosing date will be

provided along with corresponding 95% confidence intervals (CIs). The loglog transformation will be used to compute the CIs.

PFS rate of the CLL prior BTK inhibitor exposure and CLL prior PI3K inhibitor exposure cohorts will be estimated separately. PFS rate of the CLL dose ranging cohort will be estimated by dose levels.

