## **6.3. Changes from Protocol-Specified Efficacy Analyses**

The study final CSR is determined in synoptic version. The sensitivity analyses will not be performed.

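### The protocol synopsis promises iNHL results by histology in the primary PFS analysis, but the SAP pools SLL, LPL/WM and MZL without declaring the change

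*SAP*

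**What the plan says.** The synopsis (Statistical Methods) describes the primary analysis as Kaplan-Meier PFS in the full analysis set, with the Week 24 proportion reported for iNHL. Three presentation statements follow in the same paragraph. The first is "Data for subjects with iNHL will be presented by histologic subtype (ie, FL, SLL, LPL, and MZL"). The second separates the prior-BTK and prior-PI3K cohorts, and the third splits the dose-ranging cohort by dose.

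Protocol 8.2.1 repeats the second and third statements but not the first. Protocol 8.4.1 speaks of summaries by cohort, and 8.5.2.1 gives the primary analysis with no histology split. None of these sections withdraws the synopsis statement.

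The SAP groups subjects as follows: "For summary tables, unless otherwise specified, subjects will be grouped by disease indications, prior treatment status, and dose levels". The columns of Table 3-1 are CLL, FL, DLBCL, MCL, Other iNHL and Total. SAP Table 1-1 defines the fifth as "Other iNHL (LPL/WM, SLL, and MZL"). SAP 6.1.2 estimates the BTK and PI3K cohorts separately and adds "PFS rate of the CLL dose ranging cohort will be estimated by dose levels"; it says nothing on iNHL histology. On declared changes, SAP 6.3 says that the CSR will be synoptic and that "The sensitivity analyses will not be performed".

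**The concern.** Of the three presentation statements in the synopsis paragraph, two reach the SAP as PFS estimates and one disappears. Nothing marks this as a decision. A reader of the SAP would conclude that the only departure from the protocol's efficacy analyses is the loss of the sensitivity analyses.

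The omitted split concerns the one cohort that the documents themselves call mixed. Protocol 3.1.3 exempts it from futility review because the "cohort consists of 3 different histologies, accrual will continue to a maximum of 45 subjects without a Bayesian analysis", and SAP 1.2.4 gives the same reason. Protocol 2.2 also frames the primary endpoint per malignancy. If three diseases are too different to share a futility rule, a single pooled PFS rate for them is hard to interpret. A histology in which the drug works, or does not, could not be seen in the tables.

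**Working it through.** **1. What the SAP carries over from the synopsis paragraph**

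| Synopsis statement | Protocol section 8 | SAP |
|---|---|---|
| iNHL by FL, SLL, LPL, MZL | Silent | FL has a column; the other three are pooled (Table 3-1) |
| Prior BTK and prior PI3K separately | 8.2.1 | 6.1.2 and Table 3-3 |
| Dose-ranging cohort by dose | 8.2.1 | 6.1.2 and Table 3-2 |

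The grouping rule in SAP 3.2 allows exceptions where specified, but none is specified for iNHL. By-subject listings of response (SAP 6.2.2.1) do not supply a Kaplan-Meier rate by histology.

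**2. Place of the cohort in the plan's own figures**

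Protocol 8.7 gives a total of 185 to 385, and this reproduces with the non-FL iNHL cohort as one block of 45:

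- Minimum: 4×10 + 45 + 2×20 + 60 = 185.
- Maximum: 4×40 + 45 + 2×60 + 60 = 385.

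There is no quota per histology, so the mix within the 45 is open.

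**3. How far the pooled rate can move with the mix**

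The rates and splits here are assumptions chosen for illustration, not trial evidence. Assumed 24-week PFS rates are 40%, 20% and 0%, with no censoring before week 24. SAP 6.1.2 fixes the interval method: "The loglog transformation will be used to compute the CIs".

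Formula: limits = S^exp(±1.96·se), with se = √[(1−S)/(nS)] / |ln S| (Greenwood variance without censoring).

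Worked case, 9/45: S = 0.20; √[0.80/(45×0.20)] = 0.298; |ln 0.20| = 1.609; se = 0.185. The exponents are 1.438 and 0.695, so the limits are 0.20^1.438 = 9.9% and 0.20^0.695 = 32.6%.

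| Split (40% / 20% / 0%) | Progression-free | Pooled rate | 95% CI |
|---|---|---|---|
| 5 / 15 / 25 | 2+3+0 = 5 of 45 | 11.1% | 4.1% to 22.1% |
| 15 / 15 / 15 | 6+3+0 = 9 of 45 | 20.0% | 9.9% to 32.6% |
| 25 / 15 / 5 | 10+3+0 = 13 of 45 | 28.9% | 16.6% to 42.4% |

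The three diseases behave identically in every row; only the enrolment mix changes. With equal thirds, the pooled interval contains neither the 40% nor the 0% histology.

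**4. Precision of separate estimates, same formula**

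| Observed rate | n = 5 | n = 15 | n = 25 |
|---|---|---|---|
| 40% | 5.2% to 75.3% | 16.5% to 62.8% | 21.3% to 58.1% |
| 20% | 0.8% to 58.2% | 4.9% to 42.4% | 7.3% to 37.2% |

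Censoring before week 24 widens these. At S = 0, ln S does not exist and the log-log interval is undefined.

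**The case against.** The strongest reply is that the SAP follows the operative text. The histology commitment is one synopsis sentence, section 8 of the protocol does not repeat it, and the three histologies form a single cohort throughout. On that view the first defect is unevenness within the protocol. This is fair as description and should be acknowledged. But section 8 is silent, not contrary. The synopsis is part of the protocol, and unevenness is a reason to settle the point openly in the SAP.

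A second reply is imprecision: with 5 to 25 subjects per histology the intervals are wide, the trial is exploratory and the CSR is synoptic. The widths are real. However, the analysis is descriptive, and the SAP already plans PFS estimates by dose level at about 20 subjects each.

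Third, the 40/20/0% example is constructed. That stands: it shows dependence on the mix and measures no harm in this trial.

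Fourth, differences in how progression is assessed within the cohort should not be overstated. Protocol 6.20.7.7 advises at least 4 months of treatment before calling PD in LPL/WM unless evidence is compelling. That is about 4×365.25/12/7 = 17.4 weeks, before the Week 24 endpoint. Protocol 6.5 waives routine repeat scans for LPL/WM subjects without lymphadenopathy at screening. Protocol 3.2, however, keeps those without measurable disease on the same 8-weekly schedule by marrow, IgM and cryoglobulin. The method differs from that for SLL and MZL; the schedule does not. This supports separate display but does not carry the point alone.

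Finally, SAP 3.4 plans no subset analyses. That line already coexists with the finer groupings of Tables 3-2 and 3-3, so it is no obstacle.

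**Conclusion.** The point holds. The synopsis promises the iNHL results of the primary PFS analysis by four histologies; the SAP delivers FL and a pool of the other three, and SAP 6.3 does not declare the difference. Nothing elsewhere in either document restores the split.

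The consequence is limited to reporting and interpretation of the primary endpoint in a cohort of at most 45. No error rate, futility rule or sample size changes. Under the assumed rates, the pooled 24-week figure ranges from 11.1% to 28.9% through the mix alone. That range rests on the chosen rates, the chosen splits and no early censoring. The textual conclusion needs none of these assumptions.

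**What to change.** In SAP 6.1.2 and the PFS table, add the IRC-based Kaplan-Meier PFS and the 24-week rate separately for SLL, LPL/WM and MZL. Give each its n, number of events and log-log 95% CI, and keep the pooled column alongside. Showing n and events matters because no interval can be computed if a histology has nobody progression-free at week 24. SAP 3.4 can stay as it is.

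The cost is three columns from data already collected, with wide intervals that should be read as descriptive.

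If the sponsor prefers only the pooled display, SAP 6.3 should state this as a change from the synopsis and give the reason. That costs one sentence, but leaves the three diseases indistinguishable in the tables.

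Response rates by the same histologies would be a reasonable optional addition, since only LPL/WM counts VGPR and MR as response (SAP 6.2.1). The synopsis does not clearly promise that.
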